11.2 STATISTICAL ANALYSIS

All data will be analyzed by CORE at the University of Waterloo. Data analysis will be conducted using Statistica, SPSS or SAS. Descriptive statistics will be provided on information regarding baseline variables (age, gender, refractive error distribution, etc.). Analysis of variables will be conducted separately on each eye, and data will not be pooled. For assessments conducted for each eye separately, the right eye will be used for analysis if there is no difference between

eyes. If a general difference is found (e.g. for paired t-test / Wilcoxon matched pairs) between OD and OS, a comment will be provided.

The critical alpha level for statistical significance will be set at $p \leq 0.05$, with no adjustments for multiple comparisons.

All participants who were evaluated and complete all scheduled study visits will be included in the analysis cohort. In the event of missing data, individual data points will be excluded from the analysis and not extrapolated from the collected data.

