4.7 STUDY POPULATION

4.7.1 NUMBER OF PARTICIPANTS

Up to a maximum of 26 participants in each study group will be randomized, with a target of completing 17 in each of the three groups.

Groups 1 and 2 will be recruited at both CORE (Canada) and Eurolens (UK). These participants will be exposed to the study contact lens on the second day of the study. There will be competitive recruitment between the two sites and though unlikely, depending on recruitment progress, it is possible that all the subjects will be seen only at CORE (Canada) or only at Eurolens (UK). This means that a maximum of 52 and a minimum of 0 participants will be exposed to the study contact lens at each site.

Group 3, the non-lens wearing group, will all be recruited at CORE (Canada). These participants will only attend the first study visit/day and will not be exposed to the study contact lens.

Participants will be recruited using the study site records and advertising approved by the respective Office of Research Ethics (ORE). Each participant will be given a unique study specific ID number. Additionally, all participants must meet all the study inclusion and none of the exclusion criteria listed below.

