4.9 SCHEDULED AND UNSCHEDULED VISITS

4.9.2 STUDY DAY 1 (VISIT 0)

The first study day will be observational in nature for collecting comparison data across all 3 participant groups described above. There will be only one study visit (visit 0) in day 1.

Visit 0 (2.75 hours): This visit includes screening, confirmation of CL history, measurements of [REDACTED] slit-lamp biomicroscopy, [REDACTED]
[REDACTED]
[REDACTED]

At the screening, all participants who sign the informed consent letter will be assigned a study ID number. The investigator will determine participant eligibility using the inclusion and exclusion criteria. Ineligible participants will be discontinued from the study. The procedures to be performed in visit 0 are outlined below:

- The participant is expected to attend the screening visit 6-8 hours after waking. The participants in groups 1 and 2 (CL wearers) will attend, having inserted their CLs 0.5 hours after waking that day. Participants in group 3 will attend this visit with habitual spectacles, if any.
- The participant will be required to read and sign an Informed Consent Form [REDACTED] prior to enrollment. When the participant has signed the consent form, the participant will be considered to be enrolled in the study.
- Participant demographics and medical history (age, sex, medical conditions, medications, allergies).
- Contact lens history (habitual lens information and wearing habits) (N/A in group 3).
- Participants will be asked to review and sign a permission request to seek CL history from their eye care practitioner.
- Contact lens removal (N/A in group 3).
- [REDACTED]
- [REDACTED] n Slit lamp biomicroscopy.
- [REDACTED]
[REDACTED]
- Slit lamp biomicroscopy [REDACTED]
[REDACTED]
- Confirmation of study eligibility and continuation
- [REDACTED]
[REDACTED]
- [REDACTED]

- [REDACTED]
- [REDACTED]
- [REDACTED]
- [REDACTED]
- [REDACTED]
- [REDACTED]
- Day1 exit Slit lamp biomicroscopy assessments including corneal & conjunctival staining (safety measure).
- [REDACTED]

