11 STATISTICAL ANALYSIS AND DATA MANAGEMENT

11.1 SAMPLE SIZE CALCULATION

Two previous studies ^{10, 11} assessed differences in corneal response to 3-hour closed eye CL wear between low Dk/t HEMA and PMMA lenses in a group of neophytes. However, there is no

data from similar methodology and participant groups on which to calculate the sample size in the current study. A guide to the minimum sample size for Visit 2 bulbar and limbal hyperemia measures has been calculated from hyperemia data reported in a recent publication reporting objective bulbar and limbal hyperemia (using Oculus Keratograph) while wearing DDH contact lenses in habitual silicone hydrogel lens wearers.¹⁶ This data indicates that to detect an effect size of 1.2 (or 0.5 grade difference) in either bulbar or limbal hyperemia with power of 0.9 and alpha level 0.05, a minimum total sample size of 32 participants should be studied for the 2 study groups in Day 2 (Figure 1).

[figure not shown]
In this initial study to evaluate the response differences between groups it is proposed that 17 participants in each group (shown in randomized side of the graph) are studied to evaluate the size of the differences in bulbar and limbal hyperemia between groups found following lens removal and across the recovery period at each time point. If the data shows a trend of finding a difference between groups, this data can be used to plan a larger study which is powered

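### For Day 1 outcomes measured in both eyes, section 11.2 rules out combining the eyes: a valid but inefficient analysis, with no rule for which result counts if the eyes differ

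*Combined protocol and SAP*

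**What the plan says.** Section 11.2 (Statistical analysis) gives three rules on eyes, none tied to a study day or a named variable.

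- General rule: "Analysis of variables will be conducted separately on each eye, and data will not be pooled".
- For assessments made on each eye, "the right eye will be used for analysis if there is no difference between" the two eyes.
- Otherwise: "If a general difference is found (e.g. for paired t-test / Wilcoxon matched pairs) between OD and OS, a comment will be provided". Nothing says which eye, or what summary, then carries the group comparison.

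The section names no participant-level mean and no model with a participant effect.

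On Day 1, section 4.9.2 says: "The first study day will be observational in nature for collecting comparison data across all 3 participant groups described above". Section 2 makes the three-group baseline comparison of limbal and bulbar redness and of corneal vessel ingrowth a primary objective. The first hypothesis in section 3 concerns vessel ingrowth at baseline. Section 4.7.1 sets the size, "with a target of completing 17 in each of the three groups".

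**The concern.** Groups are defined in sections 4.1.1 and 4.7.2 by the person's lens history, which both eyes share. On Day 1 neither eye has been treated and neither is a control. Right and left readings of the same outcome are then two correlated measurements bearing on one between-group difference. Under section 11.2 the left eye drops out when the eyes agree, which is when combining them is easiest to justify. When they disagree, two single-eye analyses remain and the plan does not say which is the result.

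Two things are at stake: precision in a small primary comparison, and a unique pre-specified answer for each outcome.

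**Working it through.** **Inputs from the documents.** 17 completers per group (section 4.7.1). Section 11.1 plans "to detect an effect size of 1.2 (or 0.5 grade difference) in either bulbar or limbal hyperemia" "with power of 0.9 and alpha level 0.05", concluding that "a minimum total sample size of 32 participants should be studied for the 2 study groups in Day 2". The implied SD is 0.5/1.2 = 0.42 grade. This calculation is for Visit 2; there is none for Day 1.

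**Inputs assumed.** The correlation r between the eyes (within group) is not in the documents; 0.5 to 0.95 is shown. Equal variance in the two eyes and no missing eye are also assumed.

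**Step 1: reproduce the plan's figure.** A two-sample t-test (noncentral t, two-sided, standardised difference d = 1.2, alpha 0.05, power 0.9) needs 15.62 per group. Rounded up this is 16, or 32 in total, as stated. Sidedness is not stated; one-sided gives 12.63, rounded up to 13 per group (26 in total), which does not match. With 17 per group, power at d = 1.2 is 92.4%.

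**Step 2: gain from using both eyes.** If one eye has variance s², the mean of two eyes has variance s²(1 + r)/2. The standard error is multiplied by √((1 + r)/2), and 17 participants are worth 17/((1 + r)/2) single-eye participants. For r = 0.5: variance factor 0.75, SE factor 0.866, equivalent size 17/0.75 = 22.7.

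**Step 3: power for one pairwise contrast, 17 per group, two-sided 0.05.** Divide d by √((1 + r)/2). The value d = 0.8 is an illustration; d = 1.2 is the plan's Day 2 effect, borrowed because Day 1 has none.

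| r | SE reduction | Equivalent n per group | Effect detectable at 80% power | Power at d = 0.8 | Power at d = 1.2 |
|---|---|---|---|---|---|
| one eye | – | 17 | 0.99 | 61.9% | 92.4% |
| 0.95 | 1.3% | 17.4 | 0.98 | 63.0% | 93.0% |
| 0.9 | 2.5% | 17.9 | 0.97 | 64.1% | 93.6% |
| 0.8 | 5.1% | 18.9 | 0.94 | 66.4% | 94.7% |
| 0.7 | 7.8% | 20.0 | 0.91 | 68.9% | 95.7% |
| 0.5 | 13.4% | 22.7 | 0.86 | 74.3% | 97.5% |

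A three-group analysis of variance with one group shifted by 0.8 SD behaves alike: 64.3% on one eye, and 66.7%, 69.2% and 77.5% at r = 0.9, 0.8 and 0.5.

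**Step 4: what must not replace the rule.** Entering 34 eyes per group as independent observations raises the three-group type I error from 5% to about 14%, 19% and 21% at r = 0.5, 0.8 and 0.9 (simulation, 20,000 runs). A participant mean or a participant random effect avoids this.

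**The case against.** The strongest case against has four parts.

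*The analysis is valid.* One eye per participant is unbiased and holds its type I error, and the ban on pooling guards against the error in step 4. This stands in full. A reader might infer that section 11.2 biases the Day 1 comparison or inflates false positives; the documents do not support that. If significance in either eye were counted as a finding, the false-positive rate for a two-group contrast would be about 9% at r = 0.5 and 7% at r = 0.9 (simulation, 200,000 runs). But section 11.2 does not say that either eye will suffice. It only fails to say which eye counts.

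*The plan does not simply use the right eye on Day 1.* Correct. The right-eye rule depends on finding no difference between eyes, sits beside a statement that each eye is analysed separately, and is not specific to Day 1.

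*Two-eye measurement at Visit 0 is not visible.* The Visit 0 list is largely redacted, and the only legible both-eye redness entry is at Visit 6 (section 4.1.1). Section 4.1.3 speaks of measuring the main variables in the randomized eye. A reader might infer that every Day 1 interval, including that for vessel ingrowth and so the first hypothesis, is wider than the data require. The legible text does not establish this. The planned comparison of right and left eyes shows only that some variables are taken in both.

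*The gain may be trivial.* At r of 0.8 to 0.9 it is worth one or two participants per group, and at d = 1.2 power already exceeds 92%. This limits the point's importance. But d = 1.2 was set for hyperemia at Visit 2, not for Day 1 or vessel ingrowth.

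These objections narrow the point without removing it: the alternative needs no new data, accounts for the within-person correlation, and changes nothing for an outcome taken in one eye.

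**Conclusion.** The point holds as an efficiency and pre-specification improvement, limited to Visit 0 outcomes measured in both eyes. For those, the single-eye rule is valid but discards usable information on a person-level contrast, and it leaves two candidate results when the eyes differ. The precision gain is modest at r of 0.8 or above and material only if r is nearer 0.5. It rests on an assumed r, similar variance in the two eyes, and two-eye capture on Day 1, which redaction prevents confirming by outcome. It corrects no bias and no type I error in the single-eye analysis. The missing rule for differing eyes does not depend on r.

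**What to change.** In section 11.2, replace the no-pooling sentence for Day 1 only, and in the same edit specify the replacement analysis:

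- For each Visit 0 outcome measured in both eyes, the primary group comparison uses one value per participant, the mean of right and left eyes; or a mixed model with group and eye as fixed effects and a participant random effect. Name one as primary. They give the same group contrast only when both eyes are complete, so also state how a participant with one eye missing is handled; the mixed model keeps that participant.
- Single-eye results are descriptive or sensitivity analyses, whether or not the eyes differ.
- Eyes are never entered as independent observations.
- Outcomes taken in one eye are analysed on that eye.
- Averaging does not apply to Day 2, where one eye wears the lens and the other is the control (sections 4.1.1 and 4.8.4). The general right-eye rule should be reconciled separately with the randomized-eye design there.

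The cost is a few sentences in section 11.2, with no added participants, visits or measurements. A list of Visit 0 outcomes taken in both eyes would settle where the change applies.

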2 OBJECTIVES

The primary objectives of this study are:

To compare baseline data between 3 groups - *habitual wearers of DDSH / habitual wearers of DDH / non-lens wearers* - in terms of:

- Limbal & bulbar redness

- Corneal vessel ingrowth

And to compare data post closed eye lens wear in 2 groups - *habitual wearers of DDSH / habitual wearers of DDH* - in terms of:

- Limbal & bulbar redness

The primary study measures are:

- Limbal & bulbar redness (Oculus Keratograph 5)
- Corneal vessel ingrowth (slit-lamp photography & image analysis)

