3 HYPOTHESIS

The study main hypotheses are:

- 1) There will be greater corneal vessel ingrowth in habitual wearers of DDH than DDSH and non-lens wearers at baseline.
- 2) There will be greater limbal & bulbar hyperemia response following 3 hours of wearing a low Dk HEMA CL in habitual wearers of DDH than DDSH and non-lens wearers.

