4.7.2 INCLUSION AND EXCLUSION CRITERIA

A person is eligible for inclusion in the study if he/she:

1. Is between 17 and 60 years of age inclusive (age matching required between all 3 study groups), and has full legal capacity to volunteer;
2. Has had a self-reported oculo-visual examination in the last two years.
3. Has read and signed an information consent letter;
4. Is willing and able to follow instructions and maintain the appointment schedule;

5. No previous history of overnight contact lens wear or PMMA (polymethylmethacrylate) lens wear.
6. Auto-refraction vertexed spherical equivalent between +4.00 and -8.00 (prescription matching required between groups 1 & 2). This criterion is non-applicable to participants in group 3.
7. Is found to be in one of the study groups matched by age (± 5 years), ethnicity (Asian vs. non-Asian) and CL Rx (± 2.00 D) according using the following criteria:

GROUP 1: For the past (minimum) 6 months has ONLY worn spherical DDSH lenses AND prior to wearing this lens they only wore SH material lenses in the past (minimum) 3 total years.

GROUP 2: For the past (minimum) 6 months has ONLY worn spherical DDH lenses AND prior to wearing this lens they only wore H material lenses in the past (minimum) 3 total years.

GROUP 3: No previous experience of contact lens wear (no need to match Rx of this group).

8. For groups 1 & 2, currently and for at least the previous 6 months has had habitual daily disposable wear schedule of at least 8 hrs a day, 5 days a week in only one material category - either silicone hydrogel or hydrogel material. This criterion is not-applicable to participants in group 3.
9. Is willing to wear the study contact lens in the randomized eye for 3 hours of eye closure on the second study day. This criterion is not-applicable to participants in group 3.
10. Has clear and healthy corneas and anterior eye and no active* ocular disease;
11. Can achieve monocular HCVA of logMAR 0.10 or better in each eye with subjective refraction or pinhole.
12. Can achieve acceptable fit and comfort in the randomized eye with the study lens. This criterion will be confirmed at the baseline visit (V1). This criterion is not-applicable to participants in group 3.
13. Has a wearable pair of spectacles.

A person will be excluded from the study if he/she:

1. Is participating in any concurrent clinical trial;
2. Is unable/unwilling to provide permission for the study site to seek CL history from their eye care practitioner

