4.8.4 CONTACT LENS FIT AND WEAR

This is not a dispensing study. The fit of study contact lens will be evaluated on the randomly determined study eye during the baseline visit (Visit 1, Study Day 2) to ensure acceptable lens parameters and fit. After placing the study lens on the randomized eye, slit lamp examination will be conducted to confirm acceptable lens fit and comfort, and the absence of debris underneath the lens. Only participants with acceptable lens fit and comfort in the randomized eye will be eligible to continue in the study. The study lens will then remain on that eye for 3-hours and the eye will be lightly covered to keep it completely closed. Complete eye closure will be attained through the use of gauze and surgical tape, covered by a loosely-fitting ophthalmic eye patch which does not create excess pressure on the eye. The contralateral (no-lens) eye will remain open during the 3 hour period.

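### The only analysis cohort is completers, so on its natural reading lens wearers lost after Visit 0 drop out of the primary three-group Day 1 comparison, while Group 3 cannot be lost this way

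*Combined protocol and SAP*

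**What the plan says.** Section 11.2 gives a single rule for who is analysed: "All participants who were evaluated and complete all scheduled study visits will be included in the analysis cohort". The sentence after it deals with gaps in the data: "In the event of missing data, individual data points will be excluded from the analysis and not extrapolated from the collected data". Neither 11.2 nor any other section defines a separate set for Day 1.

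The first primary objective in section 2 is "To compare baseline data between 3 groups", in redness and corneal vessel ingrowth. Section 3 attaches a main hypothesis to it: "There will be greater corneal vessel ingrowth in habitual wearers of DDH than DDSH and non-lens wearers at baseline".

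Section 4.7.1 says of Group 3: "These participants will only attend the first study visit/day and will not be exposed to the study contact lens". Sections 4.1.1 and 4.9.3 give Groups 1 and 2 a second day, up to 30 days later, with Visits 1 to 6. Inclusion criterion 12 (section 4.7.2) concerns fit and comfort of the study lens. It is checked at Visit 1 and does not apply to Group 3. Section 4.8.4 states the consequence: "Only participants with acceptable lens fit and comfort in the randomized eye will be eligible to continue in the study". Section 8 lists further reasons why a participant may be discontinued.

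Section 4.7.1 allows up to 26 randomized per group, "with a target of completing 17 in each of the three groups".

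**The concern.** One cohort rule serves two comparisons with different data requirements. The Day 1 comparison needs only a Visit 0 measurement. The rule also asks wearers to come back, pass the lens check and attend six further visits. None of those later events makes the Visit 0 reading less valid.

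Two things are at stake. The first is precision: measurements already taken would go unused in a primary comparison. The second is comparability: two of the three groups would be selected on what happened after the measurement, and the third would not. Selection acting equally on both wearer groups would cancel in the contrast between them, but not in a contrast with Group 3.

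There is a smaller Day 2 counterpart. A valid Visit 2 reading would be dropped if the participant missed a later visit.

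**Working it through.** **The rule, group by group**

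| | Groups 1 and 2 | Group 3 |
|---|---|---|
| Visits needed to count as a completer | 0 to 6 (seven) | 0 (one) |
| Visit supplying the three-group data | 0 | 0 |
| Events after Visit 0 that can remove the participant | non-return, discontinuation, failed fit or comfort at Visit 1, missed later visit | none |

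The missing-data sentence removes single values. Read in order, it works inside the completer cohort and brings nobody back. The plan does not say how the two sentences fit together.

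**The plan's own sample size.** Inputs from section 11.1 are a standardized difference of 1.2 (0.5 grade, so the SD is 0.5/1.2 = 0.417 grade), power 0.9 and alpha 0.05. A two-sided two-sample t-test needs 15.62, so 16 per group and 32 in total, which matches the stated minimum. Power at 1.2 SD is 90.7% with 16 per group and 92.4% with 17. This calculation concerns Visit 2; section 11.1 gives none for Day 1.

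**Cost in precision.** The documents give no loss rate, so 5–15% of wearers lost after Visit 0 is an assumption. Seventeen completers then come from 17/0.95 = 17.9 to 17/0.85 = 20.0, that is 18 to 20 wearers with Visit 0 data. Group 3 is taken as 17. The standard error of a difference is SD × √(1/n₁ + 1/n₂).

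- Hydrogel against silicone hydrogel wearers, 17 v 17 instead of 18 v 18 or 20 v 20: √(18/17) = 1.029 and √(20/17) = 1.085, so 3–8% larger.
- One wearer group against Group 3, 17 v 17 instead of 18 v 17 or 20 v 17: √[(2/17)/(1/18 + 1/17)] = 1.014 and √[(2/17)/(1/20 + 1/17)] = 1.040, so 1–4% larger.
- With no loss, both ratios are 1.

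Difference detectable with 90% power (two-sided 0.05, noncentral t), in SD units:

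| Contrast | Completers only | All Visit 0 data, 5% lost | All Visit 0 data, 15% lost |
|---|---|---|---|
| Between wearer groups | 1.15 | 1.11 | 1.05 |
| Wearer group v Group 3 | 1.15 | 1.13 | 1.10 |

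**Possible selection, for illustration only.** Suppose lost wearers differ from retained wearers by 0.5 SD at Visit 0, in either direction. The shift in a contrast with Group 3 is the share lost × 0.5 SD: 1/18 × 0.5 = 0.028 SD and 3/20 × 0.5 = 0.075 SD. The standard error at 17 v 17 is √(2/17) = 0.343 SD, so the shift is 8–22% of one standard error. The 0.5 SD has no source in the documents. If loss is unrelated to the Visit 0 measurements, the shift is zero.

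**The case against.** **The wording does not expressly exclude anyone.** Section 11.2 says who will be included. It does not say that non-completers are barred from every analysis, and the missing-data sentence could be taken to mean available-data analysis. This stands as a limit on confidence. It does not remove the point, because this is the only cohort defined and a reader would apply it throughout. A reader might infer that the plan states outright that these data will be discarded; the text does not go that far.

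**Failing criterion 12 is an eligibility matter.** Section 4.7.1 requires every inclusion criterion to be met, and section 8 treats failure as a screening failure. That is fair for Day 2. For Day 1, the criterion concerns a lens not worn in that comparison and does not apply to Group 3, so the asymmetry remains. Non-return and later discontinuation are not covered by this argument. A reader might infer that criterion 12 itself must be amended; an analysis set can be defined without that.

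**The target is 17 completers anyway.** If it is met, Visit 2 keeps its planned precision and Day 1 has 17 per group, with no Day 1 sample size to fall short of. A reader might infer that the study becomes underpowered; it does not, since power at 1.2 SD is 92.4% with 17 v 17. The loss is relative to what the collected data could give. A reader might also take 26 randomized and 17 completing to mean that 9 Day 1 records per group will be lost. The 26 is a ceiling and may include participants who fail screening at Visit 0.

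**Bias is not shown.** This stands. No section links return, discontinuation, fit or comfort to redness or vessel ingrowth at Visit 0. A reader might infer that the contrasts with Group 3 are biased in a known direction, but the documents support only that bias is possible. On Day 2, section 4.9.3 keeps participants on site between visits, so loss after Visit 2 is probably rare and this part is secondary.

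**Conclusion.** The point holds as a minor but worthwhile correction. As naturally read, 11.2 applies to a one-visit comparison a completion rule that takes seven visits for wearers and one for Group 3, and so leaves out valid Visit 0 data from wearers lost later. Under the assumed 5–15% loss, the price is a standard error 3–8% larger between the wearer groups and 1–4% larger against Group 3; it is nil if nobody is lost. Selection bias against Group 3 is possible, but neither its size nor its direction can be found from the documents. The planned Visit 2 sample size is unaffected if the completer target is met. Confidence is moderate, because the cohort sentence does not expressly rule non-completers out of every analysis.

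**What to change.** Reword section 11.2 to define the sets by comparison.

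- **Day 1 set:** every participant who meets the criteria that apply to Day 1 (all except criterion 12, which concerns the study lens only), whose group membership is not contradicted by the lens history obtained, and who has the Visit 0 measurement, whether or not Day 2 is completed.
- **Day 2 set:** participants who completed the 3-hour closed-eye wear, which is what Hypothesis 2 refers to. Analyse each visit on those with that visit's measurement, so that a missed later visit does not remove a valid Visit 2 reading. Report early lens removals separately by group.
- **Missing data:** state that the existing sentence applies within each set, so that a missing reading removes that reading and not the participant.
- **Supporting output:** keep the completer cohort as a sensitivity analysis. Report non-completion with reasons by group, and the age, ethnicity and lens-power balance of the Day 1 set (lens power for Groups 1 and 2 only).

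The cost is a few sentences in 11.2 and one sensitivity run, with no new participants, visits or measurements. Numbers will differ slightly between analyses. Matching in the Day 1 set may be slightly looser, because lost wearers are kept alongside those recruited to reach the completer target; the balance report is there to show this.
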